1.2 Target Sample Size

The target sample size is based on the statistical estimates of adequate sample size to power the study at 95% confidence. 95% Confidence Intervals for the 12-month Transplant Rate Assumes a 50% transplant rate (Expected proportion = 0.50) at 12 months for IVIG + Rituximab

Confidence interval for proportion using normal approximation (n large)

	1	2	3
Confidence level, 1-□	0.95	0.95	0.95
1 or 2 sided interval?	2	2	2
Expected proportion, □	0.50	0.50	0.50
Distance from proportion to limit, □	0.127	0.117	0.113
n	60	70	75

We do not have a good estimate of the IVIG + Rituximab transplant rate at 12 months in this patient population. We expect the rate to be at least 50%, hopefully as high as 60 to 65%. This is based on our experience over the past 7 years where 67% of deceased donor recipients were transplanted after desensitization (Vo et al. Transplantation 2013;65:1-7). This article is included. Thus these estimates are reliable in our hands.

For estimation using a 95% confidence interval, the assumed 50% transplant rate is conservative in that the width of the 95% confidence interval will be maximum when the assumed rate is 50%, i.e. the estimate will be least precise when the assumed rate is 50%.

Table 3 shows the upper limit of the 95% confidence interval estimates of the historical transplant rate at 3 years to be about 32% (highest at 38% in 2006).

Column 3 (Distance from proportion to limit) in the above power and sample size table shows that the lower limit of the 95% confidence interval for the IVIG + Rituximab transplant rate at 12 months (assuming the rate = 50%) is about 39% [50% – 11.3% = 38.7%], which is higher than the upper limit of the 95% confidence interval for the historical rate at 3 years (even in 2006).

If the observed IVIG + Rituximab transplant rate is > 50%, then the lower level of the 95% confidence interval will be > 39% and the evidence for the effectiveness of IVIG + Rituximab will be stronger.

For example, if the observed transplant rate is 60%, then the 95% confidence interval (based on n = 75) is approximately 49% to 71%.

[As I wrote in the document: “If the observed 12-month IVIG + Rituximab transplant rate is > 50%, then the effectiveness evidence is even stronger (the lower limit of the CI will be higher).”]

If the 9-month transplant rate is 50% (or 60 to 65%) then the 12-month rate should be even higher. During the placebo controlled phase of this study, the 13/15 patients were transplanted at a mean of 7 months post treatment. (7 IVIG + Placebo v. 6 IVIG + Rituximab). The mean wait time on dialysis for this group was > 11 years prior to being entered into the study and transplanted. Our original time of assessment of transplantation

was 6M. However, with this preliminary data, we felt it better to look at 9M since this would likely be more reasonable and would give a fair assessment of the efficacy of the therapy. We feel we are being conservative with these estimates. Hopefully, this clarifies the sample size calculation issues.

Column 1: the lower limit of the CI is 0.373 or about 37% when the sample size is 60.

Column 2: the lower limit of the CI is 0.383 or about 38% when the sample size is 70.

Column 3: the lower limit of the CI is 0.387 or about 39% when the sample size is 75.

If the upper limit of the UNOS CI (historical data) is below the lower limit of the above CI, then the CI do not overlap and there is evidence that IVIG + Rituximab is more effective re the 12-month transplant rate.

Given the UNOS data for transplant rates (Table 4 & 5), 60 should be sufficient as a sample size to show benefit of the IVIG + Rituximab treatment. However, 75 patients gives a better and more robust distinction. Since we will be looking at transplant rates at 9M post-treatment, and given the vagueness of organ allocation and patient readiness issues, we feel the choice of 75 patients will provide more security for an accurate and definitive study.

If the observed 12-month IVIG + Rituximab transplant rate is > 50%, then the effectiveness evidence is even stronger (the lower limit of the CI will be higher).

1.3 Planned Efficacy Evaluations

The efficacy end points will be evaluated after all 75 patients have been enrolled into the trial. We plan to evaluate rates of deceased donor transplantation as well as conversion rate of DSA and rates of ABMR in those transplanted. The efficacy of the proposed combination of IVIG + Rituximab will be determined by the statistical methods. These evaluations will be carried out in concert with our safety monitoring that is outlined in section 9.0. The appropriate stopping points and re-evaluation points are described there as well.

1.3.1 Primary Efficacy Variables

The primary efficacy variable is the number of highly-HLA sensitized patients receiving a deceased donor transplant within 9 months after completion of the treatment. From our previous experience, the anticipated transplant rates for patients receiving IVIG + Rituximab desensitization is ~70% (49,112, 131). The rates for DD transplantation in non-treated patients based on sensitization levels is shown in Figure 15 below. Briefly, the rates of transplantation for all sensitized patients are <12% per year for the past decade. This indicates that desensitization

with IVIG + Rituximab is likely to benefit this high risk group who are otherwise unlikely to receive a life-saving transplant.

[figure not shown]

Figure 15: Data shown in figure 14 represent an analysis of 95,083 deceased donor transplants performed over the 10 year period 2000-2009. When analyzed by PRA status, one can see that <20% of all transplants performed are in highly-HLA sensitized patients. Data from the United States Renal Data Systems (usrds.gov) for 2009 also show that the wait time for a deceased donor kidney for patients with PRAs <10% is 4 years but increases to 8 years for patients with PRAs >10%. These trends have not changed over the past decade.

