STUDY OBJECTIVES:

The primary objective of this revised protocol will be to examine the safety and efficacy of IVIG 2gm/kg (maximum dose 140g) given on day#0 & day #30 plus Rituximab 1gm given on day#15. Transplanted patients will receive additional doses of Rituximab 1gm at 3 months post-transplant if DSA levels remain or become +. OR at 6M if de novo DSA occur. All transplanted patients who remain DSA-, will not receive additional Rituximab. All transplanted patients will have a protocol biopsy at 12 months.

This trial is designed to determine if Rituximab + IVIG is an effective and safe desensitization protocol and if DSAs persisting or arising at 3M and 6M post-transplant can be effectively reduced by additional doses of Rituximab. This should be reflected in reduced rates of TG for Rituximab-treated patients. This is the PRIMARY END POINT. Secondary end points include and will be evaluated based on time line in appendix A:

- Renal allograft survival at 12M

- Reduction in anti-HLA antibodies (class I/II)
- Recipient survival at 12M
- The number of acute rejection episodes
- Rates of serious infectious complications (i.e., serious infections requiring hospitalizations and/or i.v. antibiotics)
- Adverse events, toxicity assessments
- Abnormal laboratory studies: Hematology, Chemistry, Liver Function, and research tests on study
- Clinical significant abnormalities in physical examination, vital signs, weight, ECG or Chest X-ray on study
- Serial donor-specific antibody assessments
- Pre & Post-transplant determinations of CD4+/CD25+FoxP3+CD127+ & Th17 cell populations (Cedars-Sinai Patients Only).
- Pre & Post-Transplant determinations of CD19+, CD38+, CD27+ cells (Cedars-Sinai Patients Only).
- Post-Transplant biopsy at T0 and T12M assessed by Banff Criteria.
- HACA determinations at serial intervals

PRELIMINARY DATA

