This single (or multiple)-center, Phase I/II, exploratory study will use an open label design. The revision of this protocol is attributed to the failure of the placebo controlled protocol which showed a significant increase in SAEs in the IVIG + placebo group (3 antibody-mediated rejection episodes of 5 transplanted compared with 0 ABMR episodes in the IVIG + Rituximab group, $p=0.038$). The original study was put on hold and this iteration represents a redesign of the protocol to investigate the optimal dosing of Rituximab for desensitization and for modification of DSA levels post-transplant. The trial will examine the safety and efficacy of human polyclonal IgIV 10%, when given at [2.0 gm/kgx2], + Rituximab 1gm to reduce DSA to a level that is permissive for DD transplantation in 75 subjects (adults only ages ≥ 18 yrs) who are highly-HLA sensitized and are awaiting DD kidney transplant. Once transplant offers are entertained, a donor-specific crossmatch will be performed to detect anti-HLA antibodies which are associated with acute rejection or graft loss. (These anti-HLA antibodies may result naturally or from some previous pregnancy, transfusions, or prior transplants). If acceptable crossmatches and DSA levels are seen, the patients will proceed to DD transplantation. Patients receiving transplants will receive an additional dose of IVIG at transplantation (within 10 days) and will receive additional doses of Rituximab 1g) at 3M post-transplant if they remain or develop DSAs. OR at 6M if de novo DSAs occur (Fig 5 & 6). Patients who are desensitized and not transplanted within 9 M after desensitization will have completed the study and can be treated as best judged by the participating center. The protocol is shown in Figure 4 below.

[figure not shown]

Figure 4: Study Protocol for revised IVIG + Rituximab Study.

The decision to accept a DD transplant will rest entirely with the participating transplant center.

The subjects will be followed to determine the proportion who receive a transplant within 9M of completion of the infusions. In addition we will assess the transplanted patients to determine the number who sustain a viable and functioning kidney allograft for 12 months at which time a repeat study biopsy will be performed. All subjects will be evaluated on an intent-to-treat basis. The subject accrual rate will be limited to no more than five subjects per month in the initial three months to assure safety to all subjects.

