Figure 5: Pre-Transplant Desensitization Protocol for deceased donor recipients:

[figure not shown]
[figure not shown]

Figure 6 Shows the Post-Transplant Management Protocol for Patients Receiving DD Transplants.

ACCRUAL GOAL: 75 subjects

DURATION OF ACCRUAL: 24 months

DURATION OF FOLLOW-UP: 9 months for all desensitized subjects, 12 months for all transplanted subjects

THERAPY STOPPING RULES: Safety stopping rules for the study include:

The study will be put on hold and re-evaluated for safety signals if significant adverse events (serious infusion reactions, serious infections or death and or graft loss from early ABMR) are seen in three of the first 5 patients. In addition, if biopsy proven ABMR is seen in 4 of the first 10 patients entered, the study will be stopped for re-evaluation.

Efficacy Stopping Rules:

The DSMB will review cumulative safety and efficacy data according to a pre-specified schedule, not less frequently than quarterly. Based on these data (after the pre-specified data reviews, the DSMB may recommend alterations or stopping of the protocol.

CONCOMITANT MEDICATIONS: Concomitant therapy will include a standard immunosuppressive regimen of mycophenolate mofetil (CellCept[®]) at 1200 mg/m²/day given in two divided doses, Tacrolimus (Prograf[®]) given at 0.05 to 0.15 mg/kg divided twice daily, and prednisone loading dose and taper as per center protocol. Induction therapy using Campath 1H 30mg SQ/IV at the time of transplant OR Thymoglobulin[®] (total dose not to exceed 6.0mg/kg) IV per center protocol will be given to subjects on study. The safety and efficacy of Campath 1H induction therapy after desensitization with IVIG + Rituximab has been previously described for adults (11,12).

Therapy for recurrent biopsy proven rejection will be initiated as standard of care at participating institutions. The recommended initial rejection therapy will consist of pulse Solumedrol per center protocol. Alternatively, Thymoglobulin will typically be given for 5-10 days, depending on the time of return of creatinine levels to baseline. If resistant ABMR is seen, the use of IVIG +Rituximab (anti-CD20 monoclonal antibody) and/or plasmapheresis will be considered. In addition, the use of monoclonal antibodies to the complement component C5 (Eculizumab[®], Alexion, Cheshire, CT) may be used at the discretion of the investigators.

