1.0 STATISTICAL CONSIDERATIONS

1.1 IVIG + Rituximab for Desensitization

Primary Objective:

This trial is designed to determine if Rituximab + IVIG is effective in improving rates of transplantation for highly-HLA sensitized DD candidates on the UNOS waiting list over a 9M period of time after completion of treatment. Results will be compared to transplant rates in a group of age and anti-HLA antibody matched patients who remain on the UNOS wait list during the study period. This is the PRIMARY END POINT. Secondary end points include and will be evaluated based on time line in appendix A:

Transplantation rate assumptions:

- 60-65% in the IVIG + Rituximab group
- ~15% in the non-desensitized patients on UNOS wait list

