1.3.3 Methods of Analysis

Rituximab + IVIG for Desensitization

We aim to recruit 75 HS patients on the basis of a clinically relevant increase in the absolute rate of transplantation for highly-HLA sensitized deceased donor recipients of approximately 50 percentage points between the two groups during 9 months of follow-up, with an estimated event rate of 15% in the control UNOS study group. We determined that this number of patients would provide the study with a power of 95%, with a two-sided type I error of 5% and a nonadherence or loss to follow up rate of 5(or 10)%. A transplant rate of 60-70% in the intervention limb is based on our experience with desensitization in the recent years (49, 113, 131). All analyses shall be performed on the basis of the intention-to-treat principle. Patients that were transplanted outside of the study will be included in the analysis.

We shall compare the proportions of patients in the treatment group compared to the UNOS control group using time-to-event analysis with respect to outcomes such as the primary outcome (rate of transplantation) and certain secondary outcomes (such as recipient and graft survival, occurrence of rejection in the treatment group only). These outcomes shall be analyzed with the use of the log-rank test. Cox proportional-hazards regression shall be used to obtain unadjusted hazard ratios and to adjust for significant stratifying variables and to test for effect modification in all secondary analyses. Data from patients who are lost to follow-up shall be regarded as censored at the time of the last contact. Data from patients who do not receive transplantation shall be censored at end of 9 months post desensitization. We shall use Kaplan–Meier estimates of the proportion of patients with the above listed outcomes. We shall calculate the number of patients who would need to be desensitized to allow one deceased donor renal transplant from the hazard ratio and its 95% confidence interval.

For other outcomes, the Chi square or Fischer exact test shall be used if the variable is categorical, and the t-test or signed rank test if it is continuous variable.

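### The nine-month clock starts at completion of the infusions, which leaves non-completers and patients transplanted before the last infusion without a valid time zero in an analysis declared to be intention-to-treat

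*Combined protocol and SAP*

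**What the plan says.** Three places start the primary window at the end of treatment:

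- Section 1.3.1 defines the primary efficacy variable as the number of highly sensitised patients "receiving a deceased donor transplant within 9 months after completion of the treatment".
- Section 1.1 sets the primary objective "over a 9M period of time after completion of treatment".
- Study Design states: "The subjects will be followed to determine the proportion who receive a transplant within 9M of completion of the infusions".

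Study Objectives gives the course as IVIG "given on day#0 & day #30 plus Rituximab 1gm given on day#15", so completion falls about 30 days after the first infusion.

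Section 1.3.3 names time-to-event analysis for the primary outcome (log-rank, Cox, Kaplan-Meier). Data from patients without a transplant "shall be censored at end of 9 months post desensitization", and patients lost to follow-up are censored at last contact. The Duration of Follow-up entry reads "9 months for all desensitized subjects, 12 months for all transplanted subjects".

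On the analysis population, section 1.3.3 says "All analyses shall be performed on the basis of the intention-to-treat principle", and Study Design makes the same commitment for all subjects. Section 1.3.3 also allows 5 (or 10)% for nonadherence or loss to follow-up. It keeps patients transplanted outside the study in the analysis, without giving them a time origin.

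**The concern.** An intention-to-treat time-to-event analysis needs a starting point that every entered patient reaches. Completion of a three-infusion course is not such a point. Two kinds of patient are left without a rule:

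- One who stops, dies or leaves before the last infusion never reaches time zero.
- One who is transplanted before the last infusion has the event before the clock starts.

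Follow-up is also worded for desensitised subjects only, so the outcome of a non-completer might not be collected at all, and a later change to the analysis text could not recover it.

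The study is open label and compares its treated group with matched patients on the UNOS list. Starting at completion makes about 30 days of survival and continued candidacy a condition of entering the treated curve. No matching condition, and no index date, is stated for the UNOS patients. If the rule stays open, the denominator of the main result could be settled after the outcomes are known.

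**Working it through.** **Plan's own figure.** Section 1.2 uses the normal-approximation half-width 1.96 × √(p(1−p)/n). With p = 0.50 and n = 75 this is 1.96 × √(0.25/75) = 0.113, so the lower limit is 0.500 − 0.113 = 0.387, as stated in section 1.2.

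**Assumption.** The documents give no non-completion rate. The 5 (or 10)% allowance is borrowed as an assumed rate: 75 × 0.05 = 3.75, about 4 patients; 75 × 0.10 = 7.5, so 7 or 8. These patients are assumed to be followed and not transplanted.

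**Effect on the rate, with 45 transplants.**

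- All entered: 45/75 = 60.0%.
- Completers, 4 missing: 45/71 = 63.4%.
- Completers, 7 or 8 missing: 45/68 = 66.2% or 45/67 = 67.2%.

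**Effect on the lower limit, with a 50% rate in completers.**

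| Completers | Rate over 75 | Lower limit over 75 | Lower limit, completers only |
|---|---|---|---|
| 75 | 50.0% | 38.7% | 38.7% |
| 71 | 0.50 × 71/75 = 47.3% | 36.0% | 38.4% |
| 68 | 0.50 × 68/75 = 45.3% | 34.1% | 38.1% |

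For example, 0.473 − 1.96 × √(0.473 × 0.527/75) = 0.360. With 67 completers instead of 68, the limit over all 75 is 33.4%.

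Section 1.2 compares its lower limit with the upper limit of the historical rate at three years, about 32% and at most 38% (2006). In this illustration the completers-only limits still exceed 38%, while the all-entered limits fall below 38% and stay above 32%.

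**Opposite direction: early transplants.** If the 15% nine-month control rate applied at a constant hazard in the first month (an assumption), the chance of a transplant in that month is 1 − 0.85^(1/9) = 1.8%, or 75 × 0.0179 = 1.3 patients. If one of 45 transplants came early and that patient were dropped, the rate would be 44/74 = 59.5% instead of 60.0%.

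**Power.** For a two-sided 5% test against 15%, assuming 75 per group, power is 0.9976 at a 50% treated rate, 0.9932 at 47.3% and 0.9865 at 45.3%.

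**The case against.** Section 1.3.1 defines a numerator and does not restrict the denominator to completers. Since intention-to-treat is stated twice, the natural reading of a simple proportion keeps a non-completer among the 75 as not transplanted. That stands. A reader might infer that the plan excludes non-completers and so flatly contradicts its own intention-to-treat commitment. The documents do not support this; they leave these patients undefined. The objection does not rescue the time-to-event analyses, which cannot place a patient who has no time zero.

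A reader might also infer that the uncounted first month inflates the treated rate by lengthening the window. It does not. If transplants in days 0-30 are not counted, the counted window is nine months, and omitting those transplants lowers the rate. A longer window yields more events only if those early events are counted.

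The 5 (or 10)% carries no timing and covers loss as well as nonadherence, so the 63-67% range is an illustration, not a forecast. A patient lost before day 30 and before any event would be censored at last contact, and moving the origin to day 0 would leave the later Kaplan-Meier curve unchanged. The shift arises from non-completers who can still be followed. The study is described as exploratory, and the planned difference is about 50 percentage points, so the overall conclusion is unlikely to turn on this alone.

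Finally, Figures 4 to 6 and Appendix A were not available for this review, so a rule given there would not have been seen.

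**Conclusion.** The point holds as a defect in the time origin. The primary window, the censoring date and the stated follow-up all depend on completing the course, and the text reviewed gives no rule for an entered patient who does not complete it or who is transplanted before its end. Applied literally, the time-to-event estimate describes completers.

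Dropping untransplanted non-completers raises the apparent rate, by roughly 3 to 7 percentage points in the illustration. Dropping early transplants lowers it slightly. On the plan's own precision argument, the choice of population decides whether a 50% rate in completers clears the 38% historical limit; it clears 32% either way. These sizes rest on the assumed 5-10% non-completion, with those patients followed and not transplanted. The issue is bias and an undefined population; loss of power is not a material concern.

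**What to change.** Amend the protocol and section 1 as follows:

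- Set time zero at day 0 (first infusion) for every entered subject, whether or not the course is completed.
- Define the primary endpoint as deceased-donor transplant by one fixed date counted from day 0, for example day 30 plus nine months. Align the censoring date in section 1.3.3 with it.
- Count transplants during days 0-30 as events.
- Keep non-completers in the denominator and follow them to the same date, with Duration of Follow-up reworded to cover all entered subjects.
- Give the UNOS comparison the same window length and a matching index date.
- Report the completion-anchored rate as a supportive analysis.

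The cost is revised wording and outcome follow-up of a few non-completers (about 4 to 8 under the assumption above). The stated rate may be slightly less favourable. The follow-up change should be made before patients reach the end of the course, because outcomes not collected cannot be restored at analysis.

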1.3.2 Secondary Efficacy Variables

In addition to the primary efficacy variables, we will evaluate a number of secondary efficacy variables. These include donor-specific antibody testing, patient and graft survival, infectious complications, immunologic testing, protocol biopsies and rates of allograft rejection. These end points are outlined in section 2.0 and Appendix A. Data will be analyzed in the treatment group.

